8.2 Dose Changes

No dose changes are anticipated.

8.3 Storage conditions

All investigational drug supplies in the study will be stored in a secure, refrigerated (2-8°C) safe place, under the responsibility of the Investigator or other authorized individual.

8.4 Description of Blinding Method

This study will be double-blinded: neither Investigator(s), nor study participants, nor those involved in the conduct of the trial (including sponsor staff) will be aware of the treatment the participants are receiving. The appearance of B244 and vehicle dispensing containers will be identical.

8.5 Treatment Assignments:

This is a double-blind study. Participants will be assigned to study treatment in accordance with the randomization schedule generated for the allocation of B244 or vehicle prior to the initiation of the trial. Randomization will be centrally-based and performed using an appropriate IWRS (an automated randomization system).

Each participant scheduled to receive investigational product (IP) will receive a randomization number at the time of randomization. The randomization number will be used to identify the study medication kit assigned to the participant and indicate the treatment to be administered to that participant.

8.6 Treatment Compliance

Study treatment must be dispensed or administered according to procedures described herein. Only participants enrolled in the study may receive study treatment. Only authorized site personnel may supply study treatment. Participants will record use of the study medication utilizing the study diary at the time of use each day. Participants will review study medication compliance with the Investigator or designee. Any missed doses, timing, and reason for missed dose will be recorded in the eCRF. There should be no doubling of doses to make up for missed doses. If a dose is missed, the next dose of study medication should be taken as scheduled.

Each site participating in the trial will be instructed to assess subject's compliance by weighing the investigational product at the Baseline visit, Week 2 visit, and Week 4 visit and followed every time study medication is dispensed and returned per instructions below. Sites will be provided scales, which will be calibrated prior to each use. Study personnel will be instructed to record measurements into the eCRF.

All weight measurements will be performed without the safety cap. Subjects will be dispensed 2 bottles upon randomization, and each bottle will be labeled 1 and 2 with a permanent marker at the site. Unused Bottle 1 will be vortexed, primed, and weighed without the cap by the site per treatment application instructions and dispensed to the subject who will mix and apply the first dose at the site under study staff supervision. Bottle 2 will also be vortexed, primed, and weighed at the site at the time of dispense without the cap, the cap inserted back on the bottle,

and the bottle returned to its carton unused. After the first treatment application of Bottle 1, subjects will take home both bottles where they will place Bottle 1 on the counter at room temperature for in-home application twice a day until empty. Bottle 2 will be stored in the refrigerator until Bottle 1 is empty, at which point Bottle 2 will be taken out of the refrigerator, mixed per treatment application instructions, and used. Should Bottle 1 run out during a treatment application, the subject will count the number of pumps that were made with Bottle 1 and complete the remaining number of pumps needed to achieve a total of 10 pumps using Bottle 2.

At the Week 2 visit, subjects will return any empty bottle (likely Bottle 1 since each bottle should last approximately 10 days and the subject should be on Bottle 2 at the time of visit) to the site for weight measurement (without the safety cap) to confirm usage. At this visit, a third bottle of the same treatment group will be labeled as Bottle 3 and will be vortexed, primed, and weighed at the site at the time of dispense without the cap, the cap inserted back on the bottle, and the bottle returned to its carton unused. The subject will be dispensed Bottle 3 to take home and store in the refrigerator until Bottle 2 is empty, at which point Bottle 3 is taken out of the refrigerator and used on the counter until the Week 4 visit. All empty bottles returned to the site will be collected and stored by the site in ambient temperature until return to the drug depot. If the subject is still on Bottle 1 at the Week 2 visit, the site will confirm daily dosing application and retrain the subject on the appropriate use of IP application, and the subject will continue using Bottle 1 until empty, at which point Bottle 2 is taken out of the refrigerator and used on the counter until Bottle 2 is empty, after which Bottle 3 is taken out of the refrigerator and used on the counter until the Week 4 visit. Any bottle currently in use at the time of the Week 2 visit should not be returned to the site.

At the Week 4 visit, all used and unused bottles will be returned to the site for weight measurements and storage at the site in ambient temperature until return to the drug depot.

8.7 Treatment Application

Subjects will receive study drug for application throughout the study. Subjects will be instructed in the use of the spray bottle and asked to self-administer the Investigational Product following a detailed instruction on treatment application that will be shared with the sites and subjects to ensure consistency in treatment application and relation to body washing, emollient use, and other chemical exposure to skin. Key guidelines include:

- The subject should wash his/her hands before applying study treatment.
- Subjects will apply a total of 10 pumps of IP per application to all affected. areas twice-aday (i.e., 10 pumps in the morning and 10 pumps again at night).
- The subject will apply the IP to the affected area twice daily (approximately 12 hours apart) for 28 consecutive days.
- Subject should mix the bottle thoroughly per instructions provided before each application and then saturate the application area well, holding the bottle approximately 6 inches away from the skin.

- Subjects will be asked to let the product air dry after each application.
- Subjects will follow instructions provided for body washing, emollient use, and other chemical exposure to skin in relation to timing of IP application.
- The spray bottle in use may be stored at ambient temperature until used up, while additional unused bottles will be stored in the refrigerator until use. DO NOT FREEZE.
- The subject will apply the IP to the worst and largest lesions first and then apply the IP to the smaller lesions. If after covering all lesions, the total number of pumps per application has not been exhausted, subject should go back and cover the worst lesions with the remaining number of pumps. However, the total number of 10 pumps allowed should not be exceeded per application.
- Subjects will be asked not to expose the treatment kit to conditions which are unnatural or harmful to the product, such as excessive heat (temperatures over 77°F [25°C] and freezing temperatures below 32°F [0°C]). Subjects may travel with their study medication but should not leave it in a hot car, outside in the cold temperatures, etc. Subjects will also be asked not to tamper or cause damage to the IP bottle.

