6.2 Inclusion Criteria

Deviations from inclusion criteria are not allowed because they can potentially jeopardize the scientific integrity of the study, regulatory acceptability or participant safety. Therefore, adherence to the criteria as specified in the protocol is essential.

Participants eligible for enrollment in the study must meet all the following criteria:

- 1. Male and female subjects 18 to 65 years of age.
- 2. Pruritus of at least 4 weeks duration prior to the initial Screening visit and during the 2 week washout period.
 - a. Subjects using stable doses of oral H1 antihistamines at the initial Screening visit must be willing to continue these at the same doses and frequencies throughout the study inclusive of the follow-up period.
- 3. Worst Itch Numeric Rating Scale (WI-NRS) score ≥ 7 in the 24-hour period prior to the initial Screening as well as Baseline visits.
- 4. Average weekly WI-NRS score ≥6 for each week of the washout period, as recorded in the eDiary.
- 5. A history of atopic dermatitis for greater than 12 months consistent with a diagnosis of atopic dermatitis, as defined by the 2014 American Academy of Dermatology (AAD) Guidelines of Care for the Management of Atopic Dermatitis¹.
 - a. Subjects using bland emollients at the initial Screening visit will be allowed to continue to use their emollient of choice at a similar dose and frequency throughout the study, if used.
 - b. Subjects using low- to mid-potency topical corticosteroids at the initial Screening visit will be allowed to use their topical corticosteroid of choice at the same dose and frequency no more than 7 days per month throughout the study as rescue medication.
- 6. A minimum of 10% and not more than 40% of the subjects' BSA affected by atopic dermatitis (*affected* is defined by physical examination findings: erythema, edema, scaling, lichenification, excoriation, with the excoriation serving as the physical examination correlate of pruritus) at Screening and Baseline.
 - a. Subjects' BSA can include face and body OR body alone BUT NOT face alone.
- 7. An Investigator Global Assessment (IGA) score of 2-3 at Screening and Baseline.
- 8. Willing and able to complete once-daily eDiary entries within a consistent timeframe for the duration of the study and have ≥80% eDiary compliance rate during the washout period.
- 9. Judged to be in good health in the investigator's opinion.

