12 STATISTICAL CONSIDERATIONS

12.1 Sample Size

Approximately 576 subjects may be enrolled to account for 16.7% drop out rate prior to completing the study. A total of 160 evaluable subjects per group (480 total) are required to achieve at least 80% power to detect a pairwise difference of 0.65 in mean WI-NRS change from baseline to Week 4 between one of two active doses of B244 and vehicle control when assuming a standard deviation of 2.5 and applying a Dunnett Testing Method at a one-sided familywise error rate of 0.10.

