In case there are clear differences between groups in the stratified analyses, then post-hoc sensitivity analyses may be performed to control for those covariates in the appropriate statistical model. This post-hoc analysis may also include examination of outcome measures stratified by presence/absence of asthma at Baseline. Site related baseline covariates may also be analyzed post-hoc as described in Section 6.5.12. The effect of seasonality may also be investigated via seasonal pattern as one sine and one cosine function³, if applicable, including interaction with site specific covariate. Post-hoc analysis may also include examination of outcome measures that include/exclude certain lots due to aging or stratified by investigational product lot.

STATISTICAL ANALYSIS PLAN

Version 3.0 12-Jan-22

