The ANCOVA model for the primary endpoint change from Baseline to Week 4 in weekly average WI-NRS will have treatment group and Baseline weekly average WI-NRS as explanatory variables. Hypothesis testing will be done using a Dunnett Testing Method, applying pairwise comparisons of each respective B244 dose group to vehicle using a one-sided familywise error rate of 0.10. Treatment effect will be estimated as least squares means using vehicle as reference and adjusted for multiplicity according to the Dunnett Testing Method and presented with one-sided 90% CI.

Additionally, the two B244 dose groups will be compared by presenting the treatment difference estimated using least squares means.

Finally, in a separate analysis, the pooled B244 dose groups will be compared to vehicle using the same ANCOVA model.

STATISTICAL ANALYSIS PLAN

Version 3.0 12-Jan-22

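### The primary ANCOVA leaves out baseline BSA, IGA and rescue use, giving up modest precision, and no model-based analysis examines BSA although a fixed 10-pump application covers 10-40% of body surface

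*Protocol*

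**What the plan says.** **The model.** SAP 7.4.2 states that the primary ANCOVA "will have treatment group and Baseline weekly average WI-NRS as explanatory variables". The footnote to Table 14.2.2.1 repeats those two terms, and the addendum's WOCF and LOCF versions of the table keep them.

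**The other baseline factors.** SAP 7.4 plans descriptive statistics by age group, race, gender, baseline IGA, EASI, BSA band and baseline rescue use, and also by on-treatment rescue use. If these tables show evident differences, "then post-hoc sensitivity analyses may be performed to control for those covariates in the appropriate statistical model". SAP 6.4 defines the baseline values, with rescue use counted over Day -14 to -1, and SAP 7.3.3 tabulates them. Protocol 8.5 names no stratification factor for the randomisation.

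**Who enters.** Protocol 6.2 requires "A minimum of 10% and not more than 40% of the subjects" BSA to be affected, and an IGA of 2 or 3. It also provides: "Subjects using low- to mid-potency topical corticosteroids at the initial Screening visit will be allowed to use their topical corticosteroid of choice", as rescue medication on no more than 7 days per month.

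**How product is applied.** Each application is 10 pumps whatever the affected area. Protocol 8.7 sends pumps to the worst and largest lesions first, returns any left over to the worst lesions, and adds the cap: "However, the total number of 10 pumps allowed should not be exceeded per application". The same section tells subjects to wet the area thoroughly.

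**The sample size.** Protocol 12.1 sets the target: "A total of 160 evaluable subjects per group (480 total) are required to achieve at least 80% power". The effect behind it is 0.65 points on Week 4 WI-NRS change, against an SD of 2.5. Multiplicity over the two doses is handled by "applying a Dunnett Testing Method at a one-sided familywise error rate of 0.10".

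**The concern.** The SAP treats BSA, IGA and baseline rescue use as worth examining, yet keeps them out of the test that decides the trial. Covariates that predict itch change reduce residual variance only if they are in the model. Adjustment chosen after looking at subgroup tables is data-driven and can serve only as a sensitivity analysis, which is what the SAP calls it. The benefit to the primary test is therefore lost.

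The second issue is interpretation. SAP 7.4.2 compares 20.0 with 5.0 as two doses, while a fixed volume is spread over an area that varies between subjects. If benefit depends on product per area, each arm's mean averages over a range of exposures, and the plan has only descriptive tables by BSA band to show it.

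**Working it through.** **Inputs.** From Protocol 12.1 and SAP 7.1: difference 0.65, SD 2.5, 160 per arm, Dunnett with two comparisons against vehicle, one-sided familywise 0.10. From SAP 7.5.1: 0.14 g per pump, so 1.4 g per application. From Protocol 5 and 6.2: strengths 1x10^10 and 4x10^10 cells/ml, BSA 10-40%. Two assumptions are needed. The 2.5 is read as the residual SD of the two-term model. The share of that variance explained by the added covariates (R²) is set at 2%, 5% and 8%, because the documents give no figure.

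**Step 1: the plan's own figure.** The Dunnett critical value (normal approximation, correlation 0.5) is 1.577. SE = 2.5 x sqrt(2/160) = 0.2795, and 0.65/0.2795 = 2.326.

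- Power for one given dose: Φ(2.326 - 1.577) = 77.3%.
- Power to reject for at least one dose when both have a 0.65 effect: 89.5%.
- Power for one given dose at the enrolled 192 per arm: 83.4%.

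None of these equals 80% at 160 per arm. The stated minimum of 80% is met on the second reading, so the figure is not called an error here.

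**Step 2: adding covariates.** Power = Φ(0.65 / (2.5 x sqrt(1 - R²) x sqrt(2/160)) - 1.577).

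| R² (assumed) | Residual SD | Power, one given dose, 160 per arm |
|---|---|---|
| 0 | 2.500 | 77.3% |
| 0.02 | 2.475 | 78.0% |
| 0.05 | 2.437 | 79.1% |
| 0.08 | 2.398 | 80.2% |

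The gain is 0.7 to 2.9 points.

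**Step 3: chance imbalance.** Take a yes/no factor present in 40% of subjects that shifts the change score by 1 point (both assumed). Its difference in proportion between two arms of 160 has SD sqrt(2 x 0.4 x 0.6/160) = 0.055, so the estimate moves with SD 0.055. The factor's variance is 0.4 x 0.6 = 0.24, which is 0.24/6.25 = 3.8% of the outcome variance. Likewise 0.055² (0.003) is 3.8% of 0.2795² (0.078). The imbalance is thus already inside the standard error. It is the Step 2 loss in another form.

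**Step 4: bias and error rate.** In simulated trials (6,000 per scenario, 160 per arm, BSA assumed uniform on 10-40%, BSA explaining 0, 5% or 10% of variance), models with and without BSA gave mean dose effects within 0.002 of each other. The familywise error rate was about 0.09 to 0.11 under both.

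**Step 5: product per affected area.** 1.4 g over 10% BSA is 0.140 g per 1% BSA; over 40% it is 0.035 g. The ratio is 4.0. The strengths also differ by 4.0. Taking 1 g as 1 ml (this cancels in the ratio), the lower strength at 10% BSA gives 1.4x10^10/10 = 1.4x10^9 cells per 1% BSA, and the higher strength at 40% gives 5.6x10^10/40 = 1.4x10^9. SAP 6.5.11 uses a subject admitted at 50% as an example; that subject would have 0.028 g per 1%, a fivefold range.

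**Step 6: whether a BSA main effect helps with Step 5.** It does not. As an illustration, let benefit be 0.25 + 0.25 x log2(relative exposure), with exposure relative to the lower strength at 40% BSA. A low-dose subject then gains 0.25 points at 40% BSA and 0.75 at 10%; a high-dose subject at 40% also gains 0.75. The simulated mean effects for the two doses were -0.45 and -0.95 whether or not BSA was in the model. A common BSA slope across arms, vehicle included, cannot show that pattern. A treatment-by-BSA or exposure-per-area term can.

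**The case against.** The strongest case against is that the present model is valid. It includes the baseline value of the outcome, no randomisation stratum is missing from it, and the contrasts are unbiased. The gain rests on R² values with no source in the documents. BSA, IGA and rescue use already have planned descriptive tables, and the choice of three from seven named baseline strata looks like preference.

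Most of this stands as a limit on size. It does not defeat a change that uses values already derived and costs three degrees of freedom. The three chosen are affected area, the severity grade required for entry, and steroid use before randomisation. EASI combines extent and severity, so it overlaps with the first two.

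The objection also guards against four inferences that a reader might draw:

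- **That the dose-vehicle tests are biased or anti-conservative.** Step 4 shows neither.
- **That the two active arms deliver the same dose, so the 20.0 v 5.0 comparison is void.** The match holds only on average and only between the lower strength at 10% BSA and the higher strength at 40%. Because the worst lesions come first, a subject with large BSA may leave some lesions untreated instead of thinly covered. The documents give no BSA distribution and do not say that effect follows cells per area. The detailed application instruction is a separate document.
- **That 0.055 is an error on top of the standard error.** Step 3 shows that it is not.
- **That the SAP ignores BSA.** It is absent from the primary model only.

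**Conclusion.** The point holds as a modest, inexpensive improvement. Leaving out baseline BSA, IGA and rescue use forgoes 0.7 to 2.9 points of power for one given dose at 160 per arm, under the assumed 2-8% of residual variance and with 2.5 read as the residual SD. If the covariates explain nothing, nothing meaningful is lost. Validity of the primary test is not in question.

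The exposure issue is separate and concerns interpretation. Average product per affected area can differ up to fourfold across the eligible BSA range, as much as the step between strengths. The covariate adjustment would not resolve this, and the plan has no model-based analysis that would.

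**What to change.** 1. In SAP 7.4.2 and Protocol 12.5, before unblinding, specify the primary ANCOVA terms as treatment, baseline weekly average WI-NRS, baseline affected BSA (continuous), baseline IGA (2 v 3) and baseline rescue use (Yes/No, Day -14 to -1), with Dunnett applied to the adjusted means. Keep the two-term model as a sensitivity analysis. If treatment codes are already open, the adjusted model can only be supportive.
2. Do not add on-treatment rescue use. It appears in the same list of strata but is post-baseline.
3. Prespecify a supportive treatment-by-BSA analysis, or one on exposure per affected area, to help interpret 20.0 v 5.0. Report it as estimates with confidence intervals, outside the Dunnett procedure.
4. Reconcile the instruction in Protocol 8.7 to wet the area thoroughly with the 10-pump cap in the same section. No dose or number of pumps is proposed.

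The cost is one sentence for the model, one for the supportive analysis, and updated table footnotes. The adjusted model uses three more degrees of freedom: 480 - 4 = 476 residual degrees of freedom become 473. No new data are needed.

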8.8 Treatment of Investigational Product Overdose

The sponsor does not recommend specific treatment for an overdose. Washing with conventional cleanser and water will remove the product. The Investigator will use clinical judgment to treat any overdose.

8.9 Study Drug Discontinuation

Subjects will be discontinued from study drug treatment in the following events:

- The subject experiences a Grade 2 or higher treatment emergent AE that is assessed as likely related to study drug
- The subject receives treatment with an excluded therapy or has a clinically significant change in dose or frequency of allowed adjunctive therapies during the treatment period
- The female subject becomes pregnant or female partner of a male subject becomes pregnant or is breastfeeding

Discontinuation from study drug treatment may also occur for any of the following reasons:

- Subject decision to discontinue study drug treatment, or subject decision to withdraw consent from the study
- Any medical condition that may jeopardize the subject's safety if study drug is continued, in the investigator's and/or Sponsor's opinion
- Discontinuation is deemed to be in the best interest of the subject, in the investigator's and/or Sponsor's opinion

Subjects who discontinue treatment with study drug prior to completing the treatment period will have an ETD visit within 7 days after their last dose of study drug in addition to a follow-up visit

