5 STUDY DESIGN

- This is a Prospective, Vehicle Controlled, Double-Blind, Multicenter, Randomized Phase II Trial, comparing the effect of twice daily B244 applications for 4 weeks vs vehicle applications on treatment of mild to moderate pruritus associated with atopic dermatitis.
- Approximately 576 subjects may be enrolled.
- The total duration of the study will be approximately 11 weeks. Participants will report for a Screening visit and if all inclusion/exclusion criteria are met, subjects will go through a two-week washout phase (see Section 10.6.2) before reporting for a Baseline visit.
- After screening and baseline, participants will be randomized to one of two doses of B244 or vehicle application for 4 weeks.
- Randomization will be 1:1:1 so that an equal number of patients will be treated in each Arm of the study.
- All B244 randomized subjects will be treated at the dose of $1x10^{10}$ cells/ml (O.D. 5.0) or $4x10^{10}$ cells/ml (O.D. 20.0).
- Subjects must be willing and able to complete diary within a consistent time frame on a daily basis and to comply with restrictions on allowable therapies for the duration of the study.
- All subjects will attend a screening visit not more than 21 days prior to Baseline (Day 0). Subjects will be required to return to the clinic at Baseline, Day 14 (Week 2) and Day 28 (Week 4) visits. All subjects will be asked to attend a Week 8 follow-up visit 4 weeks (28 (±3) days) after the last dose of study medication.
- Subjects will apply a total of 10 pumps of IP per application across all affected areas twice-a-day (i.e. 10 pumps in the morning and 10 pumps again at night) for 4 weeks.
- Safety evaluations will consist of review of participant's medical history at screening and on-going assessment of adverse events reported throughout the study duration.

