11.6 Study Completion

A completed participant is one who has completed all study visits. Day 56 study visit is defined as the participant's last visit.

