6.5.6 Rescue Medication During Treatment Period

The treatment period (also referenced as "on-treatment") begins on date of subject's first dose and ends on Day of Visit 4 - 1, even if the subject has applied IP on Day of Visit 4.

Based on recorded use of rescue medication the following variables will be derived and normalized as described in section 7.5.4 for all subjects:

- Number of days in a month with rescue treatment (for Week 1 to Week 4 and Week 5 to Week 8)
- Number of days every 2 weeks with rescue treatment (for Day -14 to -1 for Baseline, Day 1 to Day of Visit 3 -1 for Week 2, Day of Visit 3 to Day of Visit 4 -1 for Week 4, Day of Visit 4 to Day of Visit 4 + 13 for Week 6, and Day of Visit 4 + 14 to Day of Visit 5 1 for Week 8)

Proportion of subjects with rescue treatment, and the above two variables (number of days in a month with rescue treatment and number of days every 2 weeks with rescue treatment) will be derived and normalized for subjects with recorded use of rescue medication.

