6.5.10 Visit Windows

It is expected that all visits should occur according to the protocol schedule. All visit data will be tabulated per the evaluation visit as recorded on the CRF even if the assessment is outside of the visit window. All ePRO/diary data will be tabulated per the weekly conventions defined in Section 6.5.3. In data listings, the relative day of all dates will be presented.

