7.4.3 Analysis of IGA, EASI, POEM, 5-D Pruritus Scale

The endpoints IGA, EASI, POEM, 5-D Pruritus Scale will be summarized using descriptive statistics and analyzed using a logistic regression model at each respective timepoints. Mean change from Baseline to Week 2, Week 4, and Week 8 in IGA, EASI, POEM, and 5-D Pruritus Scale, as well as IGA and EASI responders, will be analyzed for mITT and PP as described in section 7.4.

Responder status is determined by reaching a certain level of improvement as defined below. Responder status varies by outcome measure, endpoint, and visit. That is, a subject can be considered a responder at one visit, but not the next for a specific measure. Similarly, a subject can be considered a responder for one measure but not another at the same visit. Responder criteria for categorical measures are as follows:

- Proportion of subjects with an IGA 0 (clear) or 1 (almost clear) and \geq 2-point improvement from Baseline will be reported for Week 2, Week 4, and Week 8.
- Proportion of subjects with IGA 0 (clear) or 1 (almost clear) will be reported for Week 2, Week 4, and Week 8.
- Proportion of subjects with any improvement in IGA from Baseline (defined as ≥1 point change from Baseline) will be reported for Week 2, Week 4, and Week 8.
- Proportion of subjects with at least 50%, 75%, and 90% improvement in EASI (EASI-50, EASI-75, and EASI-90, respectively) from Baseline will be reported for Week 2, Week 4, and Week 8.

Each of these outcomes will be compared between treatment groups using a logistic regression model by week. Generalized estimating equations to account for repeated measures and within-subject variability may also be applied.

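### Visits after stopping study drug are not reconciled: it is unclear whether Week 4 is kept, and an early follow-up can be analysed as Week 8

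*Protocol*

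**What the plan says.** - **Protocol 8.9.** A subject who stops drug before the end of the treatment period "will have an ETD visit within 7 days after their last dose of study drug in addition to a follow-up visit". The follow-up has no stated timing, and Weeks 2 and 4 are not mentioned. Protocol 7.3 separates stopping application from refusing further visits, so such a subject may still be in the study.
- **Protocol 5.** "Subjects will be required to return to the clinic at Baseline, Day 14 (Week 2) and Day 28 (Week 4) visits". Nobody off drug is exempted. The same section adds: "All subjects will be asked to attend a Week 8 follow-up visit 4 weeks (28 (±3) days) after the last dose of study medication".
- **Protocol 11.6, 10.6.6 and Appendix A.** Here the last visit is fixed by calendar: "Day 56 study visit is defined as the participant's last visit". It is Visit 5, with a window of ±3 days. Week 4 is Day 28 ±2.
- **Protocol 10.6.8.** The ET visit is for subjects who leave the study before Day 56; the synopsis and 7.4 also link it to leaving the study. POEM, 5-D, IGA and EASI are all collected at it.
- **SAP 6.5.10.** On-site data are "tabulated per the evaluation visit as recorded on the CRF even if the assessment is outside of the visit window".
- **SAP 7.4.3.** The analysis covers "Mean change from Baseline to Week 2, Week 4, and Week 8 in IGA, EASI, POEM, and 5-D Pruritus Scale". The efficacy shells have these three visits only.
- **SAP 6.5.6 and 6.5.3.** The on-treatment period for rescue use "ends on Day of Visit 4 - 1, even if the subject has applied IP on Day of Visit 4". Diary Weeks 5 to 8 are counted from the day of Visit 4.

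**The concern.** A subject taken off drug for a related adverse event or an excluded therapy stays in the mITT population if there is one post-baseline on-site visit, and an ET visit appears to be enough. A site following 8.9 to the letter would book two visits, neither of them labelled Week 4. The ET visit calls for laboratory tests and drug collection only if it falls before Day 28, so it can be read as standing in for Visit 4. A site following section 5 would also book Day 28.

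If sites differ, the Week 4 POEM and 5-D (secondary) and IGA and EASI (exploratory) will be present or absent in early stoppers according to how the site read the protocol. The Week 8 comparison could mix different times since randomization, more so in an arm with more early stops. The analyses that depend on on-treatment rescue use also rest on a date that such a subject may not have.

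**Working it through.** **Inputs.** Protocol days, Baseline = Day 0, last dose on Day L. ET visit: Day L to L+7 (8.9). Follow-up: Day L+28 ±3, that is L+25 to L+31 (section 5). Week 4 window: Day 26-30. Week 8 window: Day 53-59 (both Appendix A).

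**1. The plan's own figure.** A completer with L = 27 or 28 has a follow-up centred on 27+28 = Day 55 or 28+28 = Day 56. This reproduces the stated Day 56, so the two anchors agree for completers.

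**2. Early stoppers and Week 8.** The follow-up can reach the Week 8 window only if L+31 ≥ 53, so L ≥ 22. For every L from 0 to 21 the whole window lies before Day 53.

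| L | Follow-up window | Days before Day 56 |
|---|---|---|
| 0 | 25-31 | 25-31 |
| 10 | 35-41 | 15-21 |
| 21 | 46-52 | 4-10 |
| 22 | 47-53 | 3-9 |

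For L = 10: 56-41 = 15 and 56-35 = 21. Under SAP 6.5.10 a visit on Day 35-41 recorded as Visit 5 goes into the Week 8 models.

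**3. Early stoppers and Week 4.** The ET visit can fall in Day 26-30 only if L+7 ≥ 26, so L ≥ 19. The follow-up can do so only if L+25 ≤ 30, so L ≤ 5. For L = 6 to 18 neither visit named in 8.9 falls in the Week 4 window. Even where a date fits, neither carries the Week 4 label, which is what the SAP uses.

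**4. ET scores.** The laboratory and vital-sign shells have Early Termination rows. The efficacy shells and the listings for the four instruments do not, and no rule places an ET score in a week.

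**5. No Visit 4.** SAP 6.5.3 (diary Weeks 5-8), 6.5.6 (end of on-treatment rescue) and 7.5.4 (rescue intervals) all need the date of Visit 4 and give no fallback. On-treatment rescue in turn defines the SAP 7.4 sub-analysis, the non-responder imputation (NRI) and the addendum's worst-observation (WOCF) analysis.

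**6. Primary endpoint.** Week 4 WI-NRS uses diary Study Days 22-28, and the diary runs to the follow-up visit. The earliest possible follow-up (L = 0) is Day 25, which is SAP Study Day 26. Study Days 22-25 then give four diary days before the visit, enough for the one-entry rule and for the four-entry sensitivity rule.

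**7. Missing-data handling.**

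| Instrument | Main model for mean change | Sensitivity analysis for missing Week 4 |
|---|---|---|
| IGA, EASI | MMRM | NRI (responders), WOCF, LOCF in ITT |
| POEM, 5-D | MMRM | none |

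For early discontinuation, NRI and WOCF apply only with an adverse event leading to discontinuation.

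**8. Number affected.** Not given. The nearest figure is the 16.7% study dropout: 0.167 × 576 = 96. That is a different event from stopping drug, so 0 to 96 is an assumed range for orientation and not a bound.

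**The case against.** The strongest reply is that nothing is cancelled. Section 8.9 adds two visits and removes none, section 5 requires Day 14 and Day 28 of everyone, and 10.6.8 keeps the ET visit for withdrawal. That stands. A reader might infer that Week 4 scores are never taken after stopping drug, or are missing by design. The documents do not support this; they are silent in one place and conflicting in others.

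Second, 8.9 gives its follow-up no label, and whether a Day 35-41 visit is recorded as Visit 5 depends on a CRF that is not among the documents. This also stands, so the Week 8 mixing is conditional. But section 5 calls the visit timed from last dose the Week 8 visit for all subjects, so that recording is the natural one.

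Third, much is already covered. MMRM uses a stopper's other recorded visits under a missing-at-random assumption, and IGA and EASI have sensitivity analyses. No listed efficacy endpoint is at Week 8, and p-values for the secondary and exploratory endpoints are declared exploratory. This lowers the stakes. It does not help POEM and 5-D, does not correct a mistimed visit, and does not define an interval that lacks its end date.

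Fourth, replacing the ET visit or the follow-up timed from last dose would remove safety assessments and the match with the 28-day adverse event window. This is right, and it limits the fix.

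**Conclusion.** The concern holds as a gap to reconcile, at modest severity. Three parts rest directly on the text: the two anchors for the last visit cannot agree for a last dose on Day 0-21; ET scores have no analysis week; and diary Weeks 5-8 and the end of on-treatment rescue have no definition without a Visit 4. Whether Week 4 is collected after stopping drug is unclear. The mistiming, 15-21 days in the Day 10 example, arises only if the follow-up is recorded as Visit 5.

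The primary Week 4 WI-NRS is largely unaffected, provided stoppers keep up the diary to follow-up. A reader might go further and infer that the missing subjects are those without benefit, or try to put a bias figure on POEM. Neither is supported: lack of benefit is not a listed reason in 8.9, and the documents give neither the number of stoppers nor how their scores differ.

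**What to change.** 1. **SAP, no new data needed.** For subjects who stop drug early, assign on-site efficacy assessments, ET assessments included, to Week 2, 4 or 8 by study day. State the windows (Appendix A's are the natural starting point) and which score counts if two fall in one window. A follow-up outside the Week 8 window is then not analysed as Week 8. Where there is no Visit 4, use Study Day 29 in place of its date; this is protocol Day 28, because the SAP counts Baseline as Day 1.
2. **Protocol clarification.** Reconcile sections 5, 7.3, 8.9, 10.6.8, 11.6 and Appendix A so that a subject who stops drug without withdrawing consent still has the Day 28 and Day 56 efficacy assessments (POEM, 5-D, IGA, EASI) and continues the diary. Leave the ET visit and the follow-up timed from last dose in place for safety.

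**Cost.** A visit-assignment rule, a protocol clarification, and extra visits for what should be a small number of subjects. Compared with the two visits in 8.9, it is two extra for a last dose on Day 6-18. It can be one on Day 0-5 (follow-up may double as Day 28) or Day 19-21 (ET may), and none from Day 22.
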